6.2.4. Derived Data

- Age (year), derived using first dose date as the reference start date and July 1st of birth year and truncated to a whole-year (integer) age. Patients whose derived age is less than 18 will have the required minimum age of 18 at informed confirmed; reporting for age, age groups, and lab ranges, however will be based on their derived age.
- Age group (<65, \geq 65 years old)
- Age group (<65, \geq 65 to <75, \geq 75 to <85, \geq 85 years old)
- Body Mass Index (BMI) (kg/m^2) = $\text{Weight}(\text{kg})/((\text{Height}(\text{cm})/100)^2)$
- BMI category (<25 kg/m^2 , \geq 25 to <30 kg/m^2 , \geq 30 kg/m^2)
- The duration of AD from diagnosis (years) = [(Date of informed consent – Date of AD diagnosis)+1]/ 365.25.
 - If year of onset is missing, duration of AD will be set as missing. Otherwise, unknown month will be taken as January, and unknown day will be taken as 01. The duration of AD will be rounded to 1 decimal place.
- Duration of AD (years) category (0 to <2 years, 2 to < 5 years, 5 to <10 years, 10 to <20 years, \geq 20 years)
- Diagnosis age (years), derived using diagnosis date as the reference start date and July 1st of birth year and truncated to a whole-integer age.
- Diagnosis age group (<18, \geq 18 to <50, \geq 50 years old)
- Change from baseline = postbaseline measurement at Visit x – baseline measurement.
 - If a baseline value is missing, it will not be imputed and the change from baseline will not be calculated.
- Percent change from baseline at Visit x:
 $((\text{Post-baseline measurement at Visit x} - \text{Baseline measurement})/\text{Baseline measurement}) * 100$.
 - If a baseline value is missing, it will not be imputed and percent change from baseline will not be calculated.
- Weight (kg) = weight (lbs) * 0.454.
- Weight category (<60 kg, \geq 60 to <100 kg, \geq 100 kg)
- Height (cm) = height (in) * 2.54.
- Cyclosporine inadequate efficacy (yes, no)
 - Set yes if the reason for discontinuation is inadequate response.

- Cyclosporine intolerance (yes, no)
 - Set **yes** if the reasons for discontinuation are: intolerance to medication or contraindication (Physician indicated cyclosporine was used and a contraindication was noted).
- Cyclosporine contraindication [ineligible] (yes, no)
 - Set to **yes** if cyclosporine never used because of a contraindication
- Cyclosporine inadvisable (yes, no)
 - Set to **yes** if the following reasons were selected for either not using the medication or discontinuing the medication:
 - Reason for not using medication: Physician decision, concern about side effects, unfavorable benefit risk, contraindication.
 - Reasons for discontinuation: inadequate response, intolerance to medication, or contraindication.
- TCNI inadequate efficacy (yes, no)
 - Set **yes** if the reason for discontinuation is inadequate response.
- TCNI intolerance (yes, no)
 - Set **yes** if the reasons for discontinuation are: intolerance to medication or contraindication (Physician indicated TCNI was used and a contraindication was noted).
- TCNI contraindication / [ineligible](yes, no)
 - Set to **yes** if TCNI never used because of a contraindication
- TCNI inadvisable (yes, no)
 - Set to **yes** if the following reasons were selected for either not using the medication or discontinuing the medication:
 - Reason for not using medication: Physician decision, concern about side effects, unfavorable benefit risk, contraindication.
 - Reasons for discontinuation: inadequate response, intolerance to medication, or contraindication.

6.3. Covariate Adjustment

The randomization to treatment groups at Week 0 (Visit 2) is stratified by disease severity (IGA) and geographic region as described in Section 5.1. Unless otherwise specified, the statistical analysis models will adjust for these stratification variables. The covariates used in the logistic model for categorical data will include the parameter value at baseline. The covariates used in the ANCOVA model for continuous data will include the parameter value at baseline. Inclusion of baseline in the model ensures treatment LSM are estimated at the same baseline value. When an MMRM analysis is performed, baseline value and baseline-by-visit interactions will be included as covariates.

6.4. Handling of Dropouts or Missing Data

Intercurrent events (ICH E9 R1) are events which occur after the treatment initiation and make it impossible to measure a variable or influence how it would be interpreted.

Depending on the estimand being addressed, different methods will be used to handle missing data as a result of intercurrent events. Intercurrent events can occur through the following:

- application of one of the censoring rules (including after permanent study drug discontinuation or after rescue therapy)
- discontinuation
- missing an intermediate visit prior to discontinuation or rescue
- lost to follow-up.

Non-censor intercurrent events are events that are not due to the application of any censoring rule, i.e., the last 3 items in the list above.

Note that as efficacy and health outcome data can accrue after a patient permanently discontinues study drug or begins rescue therapy, specific general censoring rules to the data will be applied to all efficacy and health outcome observations subsequent to these events depending on the estimand being addressed. These specific censoring rules are described below.

The *primary censoring rule* will censor efficacy and health outcome data after permanent study drug discontinuation or after rescue therapy. This censoring rule will be applied to all continuous and categorical efficacy and health outcome endpoints. This censoring rule is equivalent to using all the data up to rescue.

A *secondary censoring rule* will only censor efficacy and health outcome data after permanent study drug discontinuation. This sensitivity analysis will include all observed values up to study drug discontinuation. The secondary censoring rule will be applied to primary and key secondary efficacy and health outcome endpoints as sensitivity analyses.

Table JAHL.6.1 describes the planned imputation methods for efficacy and health outcome endpoints with associated censoring rules. Sections 6.4.1 through 6.4.5 summarize the methodology of each imputation rule.

Table JAHL.6.1. Imputation Techniques for Various Variables

Efficacy and Health Outcome Endpoints	Imputation Method
IGA(0,1), EASI75, 4-point Itch NRS improvement, EASI90, SCORAD75	NRI ^{ab} , pMI ^a , Tipping point ^a
EASI percent change, ADSS Item 2 change, Skin Pain NRS change	MMRM ^{ab} , mLOCF ^a , pMI ^a
All remaining categorical measures	NRI ^a
All remaining continuous efficacy and health outcome measures	MMRM ^a , mLOCF ^a

Abbreviations: ADSS = Atopic Dermatitis Sleep Scale; EASI = Eczema Area and Severity Index score; IGA = Investigator's Global Assessment for AD; mLOCF = modified last observation carried forward; MMRM = mixed model repeated measures; NRI = nonresponder imputation, NRS = Numeric Rating Scale; pMI = placebo multiple imputation; SCORAD = SCORing Atopic Dermatitis.

^a Analyses utilizing the primary censoring rule.

^b Analyses utilizing the secondary censoring rule.

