### 7.7.1. Prohibited Medications and Procedures

#### Prohibited Medications and Procedures Not Requiring Interruption of Investigational Product

The following therapies will not be allowed during the course of the study and, if taken by or administered to the patient, the prohibited therapy must be discontinued.

- TCS, TCNIs (e.g., tacrolimus and pimecrolimus), or topical PDE 4 inhibitor (i.e., crisaborole) except when given as rescue therapy as described in Section [7.7.3](#).
- topical antihistamines or sedating, systemic antihistamines including, but not limited to, alimemazine, chlorphenamine, clemastine, cyproheptadine, diphenhydramine, hydroxyzine, ketotifen, and promethazine
- leukotriene inhibitors (e.g., montelukast [Singulair], zafirlukast [Accolate], and zileuton [Zyflo])
- allergen immunotherapy

- phototherapy including PUVA (psoralen and ultraviolet A), ultraviolet B, tanning booth and excimer laser
- bleach baths

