### **Prohibited Medications Requiring Permanent Discontinuation of Investigational Product**

- systemic corticosteroids
- any systemic therapy, investigational or commercial (approved or off label use), used for the treatment of AD or symptoms of AD (except for antihistamines, as specified above)
- other JAK inhibitors (e.g., tofacitinib and ruxolitinib)
- systemic immunosuppressive/immunomodulatory substances, including, but not limited to, cyclosporine, methotrexate, mycophenolate mofetil, interferon  $\gamma$ , azathioprine, or biologic agents

Note: In the event that these prohibited medications were inadvertently used, agreement and documentation to continue investigational product must be sought from sponsor.

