6.4.1. Nonresponder Imputation

A nonresponder imputation (NRI) method imputes missing values as non-responses and can be justified based on the composite strategy for handling intercurrent events (ICH E9 R1). This imputation procedure assumes the effects of treatments disappear after the occurrence of an intercurrent event defined by the associated censoring rule.

All categorical endpoints will utilize the NRI method after applying the primary censoring rule to patients who permanently discontinued study drug or were rescued (described in Section 6.4). Additionally, all primary and key secondary categorical endpoints will utilize NRI after applying the secondary censoring rule as sensitivity analyses. For analyses which utilize either of the censoring methods, randomized patients without at least 1 post-baseline observation will be defined as nonresponders for all visits.

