6.11.1. Primary Outcome and Methodology

The validated Investigator's Global Assessment for AD (IGA) uses the clinical characteristics of erythema, papulation/induration, oozing/crusting and lichenification to produce a single-item score ranging from 0 to 4. The primary analysis of the study is to test the null hypotheses that neither baricitinib 4-mg nor baricitinib 2-mg is superior to placebo when evaluating the proportion of patients achieving IGA of 0 or 1 at Week 16 in the ITT population. The analysis assumes that treatment response disappears after patients are rescued or permanently discontinue from treatment. This will serve as the primary estimand. In this estimand, missing data due to the application of the primary censoring rule and the occurrence of other non-censor intercurrent events will be imputed using the NRI method described in Section [6.4.1](#).

A supplemental estimand is to test the null hypotheses that neither baricitinib 4-mg nor baricitinib 2-mg is superior to placebo when evaluating the proportion of patients achieving IGA of 0 or 1 at Week 16 in the ITT population. This analysis assumes the treatment response disappears after patients permanently discontinue from treatment. In this supplemental estimand, missing data due to the application of the secondary censoring rule and the occurrence of other non-censor intercurrent events will be imputed using the NRI method described in Section [6.4.1](#).

A logistic regression analysis as described in Section [6.2.3](#) will be used for the comparisons. The odds ratio, the corresponding 95% CIs and p-value, as well as the treatment differences and the corresponding 95% CIs, will be reported.

Multiplicity controlled analyses will be performed on the primary and key secondary (see Section [4.2.1](#)) objectives to control the overall Type I error rate at a 2-sided alpha level of 0.05. A graphical approach will be used to perform the multiplicity controlled analyses as described in Section [6.6](#).

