6.16. Protocol Deviations

Protocol deviations will be tracked by the clinical team, and their importance will be assessed by key team members during protocol deviation review meetings. Out of all important protocol deviations (IPDs) identified, a subset occurring during Period 2 with the potential to affect efficacy analyses will result in exclusion from the PP population.

Potential examples of deviations include patients who receive excluded concomitant therapy, significant non-compliance with study medication (<80% of assigned doses taken, failure to take study medication and taking incorrect study medication), patients incorrectly enrolled in the study, and patients whose data are questionable due to significant site quality or compliance issues. Refer to a separate document for the important protocol deviations.

Trial Issue Management Plan includes the categories and subcategories of important protocol deviations and whether or not these deviations will result in the exclusion of patients from per protocol set.

The number and percentage of patients having IPD(s) will be summarized within category and subcategory of deviation by treatment group for Period 2 using the ITT population. Individual patient listings of IPDs will be provided. A summary of reasons patients were excluded from the PPS will be provided by treatment group.

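### The primary censoring rule has no trigger for prohibited AD-active therapy that is neither rescue nor a reason to stop study drug (clearly phototherapy), so such a patient can count as an IGA responder

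*SAP*

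**What the plan says.** **Triggers in the SAP.** Section 6.4 says the primary censoring rule "will censor efficacy and health outcome data after permanent study drug discontinuation or after rescue therapy". Section 6.4.1 carries this into the binary endpoints: "All categorical endpoints will utilize the NRI method after applying the primary censoring rule to patients who permanently discontinued study drug or were rescued". Section 6.11.1 defines the primary estimand by the same two events: "The analysis assumes that treatment response disappears after patients are rescued or permanently discontinue from treatment". Section 6.4 lists three other intercurrent events: discontinuation, a missed intermediate visit, and loss to follow-up. It describes them in these words: "Non-censor intercurrent events are events that are not due to the application of any censoring rule, i.e., the last 3 items in the list above". Prohibited therapy is in neither group.

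**Prohibited therapy in the protocol.** Section 7.7.1 has a class of therapies that do not interrupt study drug. For that class, "if taken by or administered to the patient, the prohibited therapy must be discontinued". It includes "phototherapy including PUVA (psoralen and ultraviolet A), ultraviolet B, tanning booth and excimer laser", sedating antihistamines, and topical corticosteroids (TCS), calcineurin inhibitors (TCNIs) or crisaborole used other than as rescue. A separate class, mainly systemic agents, requires permanent discontinuation of study drug. A note to that class says that after inadvertent use "agreement and documentation to continue investigational product must be sought from sponsor".

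**Rescue.** Section 7.7.3 lists TCS, TCNIs, crisaborole and, after topical failure, oral systemic agents. Phototherapy and sedating antihistamines are not on the list. Section 5.4 makes a patient a nonresponder once rescue medication is used.

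**The concern.** A composite strategy has to say which treatments count as failure. Here a patient who uses low-potency topical rescue is a nonresponder from then on, while a patient who receives ultraviolet B and stays on study drug is scored on what the investigator sees at Week 16. The two are treated inconsistently.

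The protocol itself regards these therapies as confounders. Inclusion criterion [6] requires at least four weeks off phototherapy (tanning beds included) and off sedating antihistamines before randomization, and Section 5.4 gives reduction of confounding as the reason for washout. The same exposure late in the treatment period has no stated handling in the primary analysis.

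The same censoring rule serves all efficacy and health outcome endpoints. Sedating antihistamines bear on the itch and ADSS endpoints rather than on IGA.

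**Working it through.** **Step 1. Each therapy against the two triggers.**

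| Therapy | Stops study drug? | Listed rescue (7.7.3)? | Status under SAP 6.4 |
|---|---|---|---|
| Phototherapy | No (7.7.1) | No | Not censored; observed IGA counts |
| Sedating antihistamines | No (7.7.1) | No | Not censored; relevant to itch and ADSS |
| TCS, TCNI or crisaborole outside the rescue procedure | No (7.7.1) | Same drug classes are rescue options | SAP silent |
| Prohibited systemics | Yes (7.7.1) | Oral agents yes, including when given for another condition | Censored |
| Inadvertent prohibited systemics, sponsor agrees to continue | No (7.7.1 note) | Not stated for this case | Possibly not censored |

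Phototherapy is the clear case and inadvertent systemic use a possible one. Non-rescue topicals are unresolved.

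**Step 2. Do the planned sensitivity analyses cover it?** Per SAP Table JAHL.6.1, placebo multiple imputation, tipping point and mLOCF all use the primary censoring rule, so they inherit the gap. The secondary rule censors less. Only the per-protocol analysis might help: SAP 6.16 gives "patients who receive excluded concomitant therapy" as a potential example of a deviation, and only a subset of important deviations leads to exclusion. That analysis also drops randomized patients instead of counting them as nonresponders.

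**Step 3. Size.** Let f be the share of an arm who are IGA responders only through uncensored prohibited therapy. Relative to an analysis that counts them as nonresponders, the treatment difference shifts by

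bias = f(baricitinib) − f(placebo).

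The documents give no value of f, so these are assumptions:

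- 1% to 3% equally in both arms: bias 0.
- 2% on placebo, 1% on baricitinib: −1 point.
- 3% on placebo only: −3 points.
- 1% to 3% on baricitinib only: +1 to +3 points.

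One percent is 240 × 0.01 = 2.4 placebo patients or 120 × 0.01 = 1.2 patients on a baricitinib dose.

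**Step 4. Reproduce the power statement, then test it.** Inputs: n1 = 240 placebo and n2 = 120 per dose. SAP 6.1 has 10% vs 25% (2-mg) at two-sided 0.05. Protocol 10.1 has 10% vs 30% (10% plus 20 points) at two-sided 0.025.

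Power = Φ[(p2 − p1 − z·SE0)/SE1], where

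- SE0 = √{p̄(1 − p̄)(1/n1 + 1/n2)}, with p̄ the pooled rate;
- SE1 = √{p1(1 − p1)/n1 + p2(1 − p2)/n2}.

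Results:

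- SAP, 2-mg: p̄ = 0.15, SE0 = 0.03992, SE1 = 0.04402. (0.15 − 1.960 × 0.03992)/0.04402 = 1.630, so power is 94.8%.
- Protocol: p̄ = 0.1667, SE0 = 0.04167, SE1 = 0.04610. (0.20 − 2.241 × 0.04167)/0.04610 = 2.313, so power is 99.0%.

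Both reproduce the stated >90%. Now suppose x% of placebo and x/2% of a baricitinib arm become responders through prohibited therapy (an assumed two-to-one split):

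| x | SAP basis, 2-mg, alpha 0.05 | Protocol basis, alpha 0.025 |
|---|---|---|
| 0 | 10% vs 25%: 94.8% | 10% vs 30%: 99.0% |
| 1 | 11% vs 25.5%: 92.7% | 11% vs 30.5%: 98.4% |
| 2 | 12% vs 26%: 90.2% | 12% vs 31%: 97.6% |

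Neither document's own basis falls below 90% in this range.

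**The case against.** The strongest reply is that the protocol already handles most cases, and much of that stands.

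- **Protocol 8.2** says that a patient who requires a non-rescue agent effective for AD leaves the study before it is introduced. Study discontinuation leads to nonresponse, so planned phototherapy would usually be a failure. This narrows the gap. But the sentence sits in a list of possible reasons that may lead to discontinuation, it fits poorly with 7.7.1 (which leaves study drug running), and it does not reach use that began without the site's knowledge.
- **Systemic agents** are largely covered: study drug stops permanently under 7.7.1, and 7.7.3 counts oral systemic agents given for other conditions as rescue. Only the note on inadvertent use is left open.
- **Non-rescue topicals.** A reader might infer that these escape censoring. The documents do not show that. Rescue is open at any time, Protocol 5.4 makes any use of rescue medication a nonresponse, and the SAP is silent on use outside the procedure. Silence leaves the classification open; it does not settle it.
- **The estimand.** A reader might also infer that the primary estimand already makes any other AD therapy a failure, so that the rule contradicts it. It does not: SAP 4.1 and 6.11.1 name rescue and discontinuation only, and Protocol 10.2 keeps patients who did not follow the protocol in the ITT population. The gap is an inconsistency of principle with the handling of topical rescue, not a contradiction of the stated estimand.
- **Direction.** If placebo patients seek more outside treatment, the present rule is conservative. That is plausible, but the documents give no data on it.

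**Conclusion.** The point holds in a limited form. Read as written, the plan lets a patient given phototherapy, and possibly one kept on study drug after inadvertent systemic therapy, count as an IGA responder in the ITT primary analysis, while any topical rescue is a nonresponse. This rests on the text alone. What remains after Protocol 8.2 and 7.7.3 is mainly use that breaks the protocol, so few patients may be involved.

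Neither the size nor the sign of the bias can be established. The one-to-three-point shifts above are assumptions.

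A reader might conclude that power drops below the stated >90%. Pairing the SAP's 25% rate with alpha 0.025 gives 91.5%, 88.5% and 84.9% at x = 0, 1 and 2. But neither sample size statement makes its >90% claim for that pair, and x and the two-to-one split have no source. SAP 6.6 does start each primary test at 0.025, while SAP 6.1 states power at 0.05; that mismatch is a separate matter. No loss of the stated power is shown here.

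The change is worth making because it is cheap and because the direction is unknown: the rule should be fixed before unblinding.

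**What to change.** In SAP 6.4, name first use of prohibited AD-active therapy as an intercurrent event handled as rescue under the primary censoring rule, or at minimum add a sensitivity analysis that does so. It should cover:

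- phototherapy;
- any TCS, TCNI or crisaborole used outside the rescue procedure, so that its classification is explicit;
- prohibited systemic therapy even where study drug continues;
- sedating antihistamines, for the itch and ADSS endpoints.

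Identify cases by blinded review of concomitant medication before database lock. Protocol 7.7 already requires all concomitant medication to be recorded on the eCRF, which should supply most of what the review needs. Protocol 7.7.1 and 8.2 must also be reconciled on what happens to a patient who receives a non-rescue AD therapy; which clinical rule applies is for the sponsor to settle.

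Cost: SAP wording, a small listing review, and possibly a few more nonresponders in each arm.

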- hepatitis B virus DNA is detected with a value above limit of quantitation or 2 sequential tests return a value of below the limit of quantitation (see Section 9.4.8).
- develop a second VTE
- certain prohibited medications are taken per Section 7.7.1 (Prohibited Medications and Procedures).

If a patient discontinues investigational product for any reason, the patient is encouraged to remain in the study through Week 16 (Visit 8) and follow the regular visit schedule to provide

the primary efficacy and safety data. Patients discontinuing from the investigational product prematurely for any reason should complete AE and other follow-up procedures per Section 2 (Schedule of Activities), Section 9.2 (Adverse Events), and Section 9.4 (Safety) of this protocol.

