#### **Missing data imputation:**

1. Nonresponder imputation (NRI): All patients who discontinue the study or the study treatment at any time for any reason will be defined as nonresponders for the NRI analysis for categorical variables such as IGA 0/1 or EASI 50/75/90 after discontinuation and onward. Patients who receive rescue therapy will be analyzed as nonresponders after rescue and onward. An additional analysis will be performed that includes all available data whether rescue medication was given or not.
2. MMRM: Continuous variables such as EASI and SCORAD scores will be assumed to be missing after rescue or discontinuation and then an MMRM analysis will be performed. An additional analysis will be performed that includes all available data whether rescue medication was given or not.
3. Last observed carried forward (LOCF): An additional analysis will be performed that uses the last observed value on or prior to discontinuation or rescue therapy. This will

then be analyzed using a logistic model for categorical variables or ANCOVA for continuous variables as described above.

Additional sensitivity analyses for the primary and key secondary endpoints such as tipping point analyses as well as a reference based multiple imputation method may be done and will be specified in the SAP.

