The lower bound of Week 15 diary window is defined as Day 99. The upper bound of the Week 15 diary window is the minimum of either Day 105 or the lower bound of the Week 16 diary window -1. Consequently, Week 15 may be less than 4 days if the Week 16 scheduled visit is before Day 112. Moreover, as Week 15 diary window cannot exceed 7 days, there could be daily assessments between Weeks 15 and 16 diary windows that do not fall into a diary window. If after constructing the diary windows, there are fewer than 4 non-missing values the mean for that particular window is missing and subject to imputation rules.

The postbaseline value of the actigraphy analyses will be analyzed similarly through Week 4 (Visit 5) or early discontinuation but will include time. Thus, Week 1 will be the mean of the 7 days of actigraphy events which has a start date and time occurring within 168 hours of the date and time of first study drug administration. The Week 2, Week 3 and Week 4 scores will be similarly defined. If there are less than 4 non-missing assessments occurring in at least 4 separate 24-hour increments, the weekly interval will be missing. Furthermore, as some analyses require use of the primary censoring rule, assessments collected on the day of rescue or afterwards will be excluded from the weekly visit interval calculation when implementing the rule for daily diary and actigraphy analyses. If, after exclusion of these records, there are less than 4 non-missing assessments, the weekly interval which implements the primary censoring rule will be missing. The post-study follow-up weekly score for daily diaries will be calculated as the mean of the 7 days prior to the follow-up visit which occur after last dose of study treatment.

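### The SAP's gloss on the primary censoring rule, and its weekly diary derivation, omit permanent drug discontinuation, so off-drug diary data could enter the ADSS Item 2 and Skin Pain analyses

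*SAP*

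**What the plan says.** SAP 6.4 states that the primary rule "will censor efficacy and health outcome data after permanent study drug discontinuation or after rescue therapy" and applies it to every continuous and categorical efficacy and health outcome endpoint. Two sentences later the same paragraph says: "This censoring rule is equivalent to using all the data up to rescue". The secondary rule, used for sensitivity analyses, "will only censor efficacy and health outcome data after permanent study drug discontinuation".

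SAP 6.2.2 explains how weekly means are built for the daily diaries and actigraphy. Under the primary rule, "assessments collected on the day of rescue or afterwards will be excluded from the weekly visit interval calculation when implementing the rule". If fewer than four assessments then remain, "the weekly interval which implements the primary censoring rule will be missing". Drug discontinuation is not mentioned there.

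The SCORAD75 line of the placebo multiple imputation seed table (Table JAHL.6.2) also describes the primary rule as data up to rescue.

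Protocol 10.3.1, under missing data imputation, names both events. For categorical variables, "All patients who discontinue the study or the study treatment at any time for any reason will be defined as nonresponders", and rescued patients are treated likewise. Continuous variables are set to missing after rescue or discontinuation. Protocol 8.1.2 says that a patient who stops investigational product "is encouraged to remain in the study through Week 16 (Visit 8) and follow the regular visit schedule", and Protocol 5.1.2 says much the same.

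**The concern.** The gloss and the definition in 6.4 agree only if nobody stops drug without also being rescued. The plan does not expect that. Protocol 8.1.2 lists reasons for permanent discontinuation that have nothing to do with rescue, such as patient request, laboratory thresholds and pregnancy. SAP 6.4 itself notes that data can accrue after drug is stopped.

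The gloss alone would be a slip of wording. It matters because 6.2.2, the text a programmer would open to build the weekly means, has the same gap and presents the result as the primary rule in operation. A literal implementation would treat diary days recorded off drug as observed on-treatment data.

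For the MMRM endpoints this cuts against SAP 6.4.2, which describes the target as the effect had all patients stayed on their assigned treatment. Visit-based endpoints would be censored at discontinuation and weekly diary endpoints would not, so key secondaries in the same testing graph would answer different questions.

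**Working it through.** No stated figure is in dispute, so the check compares the texts.

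**Step 1. Patient types under each statement of the rule.**

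| Patient | Definition in 6.4 | Gloss in 6.4 and diary sentence in 6.2.2 | Secondary rule |
|---|---|---|---|
| Neither event | kept | kept | kept |
| Rescued, stays on drug | censored | censored | kept |
| Stops drug, never rescued | censored | **kept** | censored |
| Both events | censored from the earlier | censored from rescue | censored from the stop |

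The third row is the discrepancy. In the fourth row, a patient who stops drug first and is rescued later would also keep the days in between. On the rescue-only wording, the primary rule keeps patients whom the secondary rule censors. The secondary rule is meant to relax the primary rule by ignoring rescue, so moving between the two would then change two things at once.

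**Step 2. Where the rest of the plan stands.** These places name discontinuation as well as rescue:
- the primary objective (SAP 4.1);
- the daily-itch Cox analysis (SAP 6.2.3);
- nonresponder imputation (SAP 6.4.1);
- placebo multiple imputation, step 4 (SAP 6.4.4);
- the primary and secondary estimands (SAP 6.11.1 and 6.11.2);
- Protocol 10.3.1.

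The rescue-only wording appears in the 6.4 gloss, the 6.2.2 weekly-mean sentence and the SCORAD75 seed line.

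**Step 3. Hypotheses reached (SAP 6.6).** There are 12 endpoints x 3 doses = 36 hypotheses. Those built on weekly diary means are:
- ADSS Item 2, Weeks 1 and 16: 2 x 3 = 6, continuous, MMRM
- Skin Pain NRS, Week 16: 1 x 3 = 3, continuous, MMRM
- 4-point Itch NRS, Weeks 1, 2, 4 and 16: 4 x 3 = 12, categorical, nonresponder imputation

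The continuous set is 6 + 3 = 9 of 36. The nonresponder wording in 6.4.1 does not cover these. For the 12 Itch hypotheses, 6.4.1 names both events and contradicts a literal reading of 6.2.2.

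**Step 4. Timing.** Three of the 9 are at Week 1 (ADSS Item 2 x 3 doses). To matter there, a patient must stop permanently within Days 1 to 7 and go on recording, so little effect is likely. The other 6 are at Week 16. Section 6.2.3 puts every weekly mean up to Week 16 into the diary MMRM, so all off-drug weeks would enter that model.

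**Step 5. Size.** The documents give no rate of stopping drug without rescue. The following is assumption only. If 2% to 10% of an arm did so, that would be 0.02 x 120 = 2.4 to 0.10 x 120 = 12 patients per baricitinib arm, and 4.8 to 24 of the 240 on placebo. If 6.2.2 were followed over 6.4.1 for Itch, and 10% to 50% of these patients met the 4-point definition, one arm's response rate would rise by 0.02 x 0.10 = 0.2 points to 0.10 x 0.50 = 5.0 points. The effect on a treatment difference depends on both arms and could go either way. For the MMRM endpoints, the shift depends on the share affected and on how far their off-drug scores differ from what the model would predict had they stayed on drug. Neither is given.

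**The case against.** The strongest reply is that the operative rule is already clear. The definition in 6.4 names both events and covers all health outcome endpoints, which includes the diaries. Most other sections agree with it, and 6.11.2 points through Table JAHL.6.1 to ADSS Item 2 and Skin Pain as well. The rescue-only reading also makes the secondary rule incoherent, and a loose gloss should not outrank a definition two sentences earlier. Section 6.2.2 gives no discontinuation step for the secondary rule either, although Table JAHL.6.1 applies that rule to these endpoints. The 6.2.2 sentence may therefore only settle same-day rescue records and leave discontinuation to 6.4.

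Most of this stands as evidence of intent. It does not remove the problem, because 6.2.2 is specific, operational and presented as the implementation of the primary rule. A programmer who codes it faithfully departs from the definition.

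Three stronger readings are tempting and are not supported:
- **Off-drug IGA or EASI would count as observed.** They are visit-based, so the weekly-mean derivation does not reach them, and SAP 6.4.1, 6.11.1, 6.11.2 and Protocol 10.3.1 name discontinuation.
- **All 12 + 9 = 21 diary hypotheses are equally open.** Section 6.4.1 gives explicit contrary text for the 12 categorical Itch hypotheses. Section 6.2.2 is also not the only text on diary censoring, because the daily-itch Cox analysis in 6.2.3 names both events.
- **A power loss or a bias in a given direction can be calculated.** That would need rates the documents lack, and the standard error of the planned IGA comparison does not apply to these endpoints.

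**Conclusion.** The point holds, within limits. The gloss in 6.4 is wrong as written, and the weekly diary and actigraphy derivation in 6.2.2 repeats the omission. If 6.2.2 is coded literally, patients who stop drug without rescue and keep recording contribute off-drug data to the weekly means, contrary to the 6.4 definition, the 6.4.2 estimand and Protocol 10.3.1.

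The main exposure is 9 of 36 controlled hypotheses, of which the 6 at Week 16 matter most. Another 12 (4-point Itch) carry a conflict between 6.2.2 and 6.4.1. IGA and EASI are unaffected. The size and direction of any bias cannot be derived from the documents. This is a text correction that restores the plan's own definition, and it leaves the design and sample size as they are.

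**What to change.** 1. In SAP 6.4, delete the sentence that equates the primary rule with data up to rescue, or reword it to say that the rule uses all data up to the earlier of rescue and permanent study drug discontinuation.
2. In SAP 6.2.2, have the primary rule exclude diary and actigraphy assessments made on or after the day of rescue, or after permanent study drug discontinuation, whichever comes first. State that the secondary rule excludes only those made after discontinuation.
3. In Table JAHL.6.2, align the SCORAD75 line with the corrected wording, for consistency.

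The cost is two sentences of SAP text, one table entry, and one further date in the weekly-mean program. No new data, method or sample-size change is involved. Done before unblinding, it also removes any later choice between two derivations.
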